### 4 STUDY DESIGN

During this phase of the trial, 56 subjects will be assigned to the fitbit only group (control) or the PACE-Life walking group (intervention). The exercise intervention, PACE-Life, will last for 16 weeks and includes both group walks and independent walks (done at a location of the subject's choosing). Subjects will be asked to complete a total of 5 in-person, or virtual assessments at screening, baseline, mid-point, post-test, and 1-month follow-up.

### 4.1 INTERVENTION

Groups will occur twice per week, starting at 15-minute walking sessions, and increasing to 30 minutes sessions over the course of the intervention. The intensity, of both group walks and home-based walks will increase throughout this intervention in a stepwise fashion to create an exercise dose response to maximize impact on CRF. The rationale for this plan hinges on both the importance of maintaining cohesion and social interaction as well as the practicality concerns regarding sustainability. Furthermore, we tested a 2x/week group schedule in the pilot with high attendance rates and feedback (overall attendance: 84%). The overviews of in-person and virtual formats are given below:

Weeks	# of Clinic-based Group Sessions	Duration of Group Sessions	# of Home- based Sessions	Duration of Home- based Sessions	Intensity
1-3	2	30 Minutes	0	30 Minutes	50-60% of HRR
4-6	2	30 Minutes	0	30 Minutes	50-65% of HRR
7-9	2	30 Minutes	1	30 Minutes	60-65% of HRR
10-12	2	30 Minutes	1	30 Minutes	65-70% of HRR
13-15	2	30 Minutes	2	30 Minutes	65-70% of HRR
16-18	2	30 Minutes	2	30 Minutes	65-70% of HRR
19-21	2	30 Minutes	3	30 Minutes	70% of HRR
22-24	2	30 Minutes	3	30 Minutes	70% of HRR

Week	# of Virtual Group Sessions	Links to Virtual Group Sessions	Duration of Virtual Group Sessions	# of Independent Walks	Duration of Independent Sessions	Intensity	Pe Ex
1	2	1st group: https://www.youtube.com/watch?v=cvrcgZ25MWw 2nd group: https://www.youtube.com/watch?v=iBAjNQODSVo	15 minutes	0	15 minutes	50-60% of HRR	
2	2	1 st group: https://www.youtube.com/watch?v=tW9IY48x1bc 2 nd group: https://www.youtube.com/watch?v=u08lo0bESJc	15 minutes	0	15 minutes	50-60% of HRR	
3	2	1st group: https://www.youtube.com/watch?v=wQrV75N2BrI 2nd group: https://www.youtube.com/watch?v=-SSYX8sIOmM	20 minutes	1	20 minutes	50-65% of HRR	
4	2	1 st group: https://www.youtube.com/watch?v=kqaNUjTR70A 2 nd group: https://www.youtube.com/watch?v=m9yI2LGZRE0	20 minutes	1	20 minutes	50-65% of HRR	
5	2	1 st group: https://www.youtube.com/watch?v=kqaNUjTR70A 2 nd group: https://www.youtube.com/watch?v=UhpOl71brYI	20 minutes	1	20 minutes	60-65% of HRR	
6	2	1st group: https://www.youtube.com/watch?v=UXS_fFeGAlc 2nd group: https://www.youtube.com/watch?v=0KPpICARPGQ	20 minutes	1	20 minutes	60-65% of HRR	
7	2	1st group: https://www.youtube.com/watch?v=_UabUNrjSE4 2nd group: https://www.youtube.com/watch?v=GfiL9jPXMFE	25 minutes	2	25 minutes	60-65% of HRR	

	•						
8	2	1st group: https://www.youtube.com/watch?v=v4YyCdTf9BM 2nd group: https://www.youtube.com/watch?v=RImvimPo5u0	25 minutes	2	25 minutes	60-65% of HRR	
9	2	1st group: https://www.youtube.com/watch?v=hXhudyDRX8M 2nd group: https://www.youtube.com/watch?v=baO6jTGmNFs	25 minutes	2	25 minutes	60-65% of HRR	
10	2	1st group: https://www.youtube.com/watch?v=RP0Q8geTcJc 2nd group: https://www.youtube.com/watch?v=vUQXg5V7y2Q	30 minutes	2	30 minutes	60-65% of HRR	
11	2	1st group: https://www.youtube.com/watch?v=enYITYwvPAQ 2nd group: https://www.youtube.com/watch?v=jf1Q8nep6JU	30 minutes	2	30 minutes	60-65% of HRR	
12	2	1st group: https://www.youtube.com/watch?v=p2ggHwtb-Zg 2nd group: https://www.youtube.com/watch?v=R3AUw3-jtEo	30 minutes	2	30 minutes	60-65% of HRR	
13	2	1st group: https://www.youtube.com/watch?v=l5uilZNoaAU 2nd group: https://www.youtube.com/watch?v=HSoDitXs35w	30 minutes	3	30 minutes	65-70% of HRR	
14	2	1st group: https://www.youtube.com/watch?v=kp67VFhbpsQ 2nd group: https://www.youtube.com/watch?v=uUki7XMG0iA	30 minutes	3	30 minutes	65-70% of HRR	
15	2	1stgroup: https://www.youtube.com/watch?v=enYITYwvPAQ&list 2nd group: https://www.youtube.com/watch?v=RP0Q8geTcJc	30 minutes	3	30 minutes	65-70% of HRR	
16	2	1st group: https://www.youtube.com/watch?v=p2ggHwtb- 2nd group: https://www.youtube.com/watch?v=wwn3YJyOzdY	30 minutes	3	30 minutes	65-70% of HRR	

PACE-life will be integrated into the STEP outpatient clinics in Raleigh, NC and Carrboro, NC. The group walks will occur in the surrounding area around the clinics on sidewalks, bike trails, and residential streets. Goal setting groups and all assessments will take place in a conference room at the clinic. Virtual walking sessions will take place on the UNC HIPAA and Security-compliant Zoom video calls and can be completed at subjects' homes.

### 4.1.1 GOAL-SETTING

Goal-setting will include setting goals for the upcoming week in terms of number of steps as well as how many intensity walks (at specified heart rate) that individuals plan to complete. Goal-setting materials draw upon SMART (specific, measurable, achievable, relevant, and time-based) principles as well as implementation intentions (i.e., if-then plans) and mental contrasting. Specifically, subjects will be asked to imagine what the best thing would be about walking/exercise more and then identify the biggest barriers. They will then be encouraged to create if-then plans about how to manage barriers to exercising more. This procedure has been extensively examined in social psychology research and has been shown to be successful in helping individuals increase their exercise (93). Goal-setting groups will be audiotaped and subsequently coded for fidelity to the protocol.

### 4.1.2 FITBITS

All subjects will be provided with a Fitbit that is labeled with a subject number. All Fitbits are paired to a Fitbit account with the username ([contact]) and password (pacelife; or

PacelifeIDnumber!). Data from Fitbit devices can be synced to the corresponding account and accessed through Fitbit.com. Subjects will be provided information about their accounts should they want to look at the data but will be asked not to change any of the settings as we will be using data for tracking steps/day and minutes spent walking. No identifying information will be inputted in the Fitbit.com account for subjects.

### 4.1.3 Tablets & Data Plans

All subjects assigned to the PACE-Life group will be given a tablet labeled with their subject number. If subjects do not own a smartphone or personal computer, they may use the tablet for syncing their Fitbit devices. The tablets will also be used to join virtual walking sessions. Subjects will be provided information about their devices but will be asked not to change any of the settings (or download new apps). No identifying information will be inputted in the subjects' tablet. Additionally, subjects who do not have reliable wifi in their homes, will be given a monthly data plan to ensure proper connectivity throughout the study.

### 4.2 STUDY PROCEDURES AND MEASUREMENTS

### 4.2.1 SCREENING VISIT

The following measures will be examined at screening:

- Demographics- We will collect information on age, sex, ancestry, education, parent education, smoking, substance use, current medications, duration of outpatient treatment, and diet.
- Intelligence- In adherence with our inclusion criteria that subjects must have an IQ greater than 70, the Wechsler Abbreviated Scale of Intelligence (WASI) will be administered. Subjects participating during the COVID-19 pandemic must have a reading level above the 4th grade, the Wide Range Achievement Test (WRAT) will be administered.
- Medical History- A licensed physician will complete the Medical History and Physical Exam
  Form. They will also complete a 10 minute physical to ensure health. Subjects participating
  during the COVID-19 pandemic will receive medical clearance from a General Practitioner (GP).
  Medical Clearance forms will be sent to and received from providers through the EPIC system.
- Current Physical Activity- In order to ensure that subjects are healthy enough to begin the walking program, subjects will complete the Physical Activity Readiness Questionnaire (PAR-Q).
- Diagnosis-The Mini International Neuropsychiatric Interview (MINI) will be utilized to assess symptoms. The MINI is a semi-structured interview that assesses for DSM diagnoses. The MINI will be used to verify that subjects have a schizophrenia spectrum diagnosis before they are enrolled in the study. Raters will be trained to conduct the MINI to a gold standard of reliability (i.e., intraclass correlation > .80).

### 4.2.2 BASELINE, MID-POINT, POST-TEST, 1 MONTH FOLLOW-UP

The following measures will be examined at the baseline, mid-point, post-test, and 1 month follow-up study visits:

- Demographics- We will collect information on age, sex, ancestry, education, parent education, smoking, substance use, current medications, duration of outpatient treatment, and diet.
- Minutes Spent Walking- We will utilize data recorded from Fitbits to assess minutes spent
  walking (by syncing Fitbits to corresponding Fitbit.com accounts and loading deidentified data
  onto study laptops).

- The Short Form International Physical Activity Questionnaire (IPAQ), a valid self-report
  measure, to assess changes in physical activity. The IPAQ Short Form is a four-item scale that
  assesses frequency and duration of walking, moderate-intensity exercise, vigorous-activity
  exercise, and sitting.
- Steps/day. We will also collect daily step numbers using Fitbit data downloaded onto study laptops from Fitbit.com at group sessions.
- Cardiorespiratory fitness (CRF)- CRF will be measured using the 6-minute walk test (6MWT) during which individuals are asked to walk continuously for six minutes on a flat, indoor surface around cones (separated by 100ft) and the primary outcome is the total distance walked. The 6MWT is recommended for use with sedentary individuals and to evaluate the impact of an exercise intervention. Moreover, the 6MWT has been successfully administered to individuals with SSDs, including those in our pilot trial. As a result, we plan to utilize the 6MWT as our primary measure of CRF. Supplemental CRF measures will also be used. CRF will be calculated using an equation by Jackson, A. S., et al. 1990 (119) that includes recent weight and height for the calculation of BMI, gender, self-reported physical activity level, and age. Finally, participants will complete a Chair-Rise Task, where subjects will sit and stand from a chair for 30 seconds, and the 2-minute Step Test, where subjects will walk in place with their knees raising to hipheight, to measure CRF.
- Self-determination Basic Needs. The self-determination basic needs of autonomy, relatedness, and competence will be measured with two scales. The Basic Psychological Need Scale-in General is a self-report measure that assesses general satisfaction with autonomy, relatedness, and competence. Three subscale scores are produced. The Basic Psychological Needs in Exercise Scale (BPNES) is self-report scale that measures the extent to which basic needs are satisfied through exercise.
- Symptoms- the Positive and Negative Syndrome Scale (PANSS) will be utilized to assess
  symptoms specifically present in schizophrenia spectrum disorders. The PANSS is a semistructured interview assessing positive symptoms, negative symptoms, and general
  psychopathology symptoms. Raters will be trained to conduct the PANSS to a gold standard of
  reliability (i.e., intraclass correlation > .80)
- Resting Systolic/Diastolic Blood Pressure and RHR will be assessed following standardized procedures at the STEP clinic. Individuals with SSDs will be placed in a sitting position in a quiet room, with lights dimmed, and will be asked to remain quiet and relaxed with their eyes closed while avoiding movement for approximately 10 minutes. After 10 minutes, research team members will assess their RHR via palpation for 1 minute. Following the assessment of RHR, resting BP will be assessed using an automated blood pressure device following the manufacture standard procedures. Given the high rates of hypertension in this population, the assessments of blood pressure changes throughout this exercise intervention are significant indicators of potential benefits of exercise on improvements in physical health. Further, given the sedentary lifestyle of many individuals with SSD, changes in RHR upon the initiation of exercise is a valuable indicator of fitness and physical health. Due to COVID-19, all subjects completing virtual study visits will have these measures assessed at their homes, on UNC-CH campus (Fetzer Hall), or at the Wake STEP Clinic in Raleigh, NC.

- Autonomous Motivation- Given the available research indicating that autonomous motivation is related to negative symptoms and subsequent engagement, maintenance, and adoption of exercise in individuals with SSDs, we will measure this construct with The Behavioral Regulation in Exercise Questionnaire-2 (BREQ-2).
- Enjoyment of Walking- Given that enjoyment of the walking program can impact adherence to the treatment, we will measure this construct with the Physical Activity Enjoyment Scale (PACES).
- Planned Behavior- Available research has shown that intentions, self-efficacy, attitudes and norms are correlated to adherence in exercise. All items are derived from established measures of theory of planned behavior variables (e.g., Conner & Sparks, 2015). Responses are all on 7point scales. The order of items would be randomized.
- Loneliness: The UCLA Loneliness Scale is a brief self-report measure that will be used to assess this construct.
- Weight, BMI, and Waist/hip Circumference- We will measure weight, BMI, and waist/hip circumference at all assessments using the scale and measuring tape located at the STEP clinic.
- Exit Surveys on PACE-life- At the conclusion of the open trial, we will administer a brief questionnaire to the subjects regarding satisfaction and acceptability that will have both forced choice and open-ended questions (End of Study Survey & CSQ-8).

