### **PROTOCOL SYNOPSIS**

Study Title	Targeting Physical Health in Schizophrenia: Physical Activity Can Enhance life (PACE-Life)		
Funder	National Institutes of Mental Health		
Clinical Phase	Phase II		
Study Rationale	The purpose of the PACE-Life trial is to develop and test the feasibility of an exercise intervention that combines group walking, activity tracking, and heart rate monitoring, and determine the effectiveness of this intervention on the physical and mental health for individuals with schizophrenia spectrum disorders.		
Study Objective(s)	
 
Feasibility- Can PACE-life be delivered within this treatment setting?
 
Tolerability- How well is PACE-life accepted by the subjects?
 
Intervention adherence
 
Evaluation of PACE-life
 
		
Test Article(s) (If Applicable)	Fitbits Charge 3 devices, worn on the wrist, will be utilized to track daily steps, minutes spent walking, and monitor HR throughout exercise sessions. These devices will also be used to facilitate the		
Study Design	individualized/home-based component and goal-setting.  This is a two arm (fitbit only vs. fitbit + exercise intervention group), randomized controlled trial with 56 subjects (multiple groups occurring consecutively ranging from 13-18 participants).		
Subject Population key criteria for Inclusion and Exclusion:	
 
Inclusion Criteria
 
DSM-V diagnosis of a SSD (Schizophrenia, Schizoaffective Disorder, Brief Psychotic Disorder, Schizophreniform Disorder, and Unspecified Schizophrenia Spectrum and Other Psychotic Disorder)
 
Between the ages of 18-65, both genders, and any ancestry;
 
IQ>70 and/or reading level at, or above the 4th grade. IQ will be assessed using the Wechsler Abbreviated Scale of Intelligence (WASI) and the Wide Range Achievement Test (WRAT).
 
No hospitalizations for psychiatric reasons in the last 3 months
 
Clinically stable (no psychiatric medication changes within the past month)
 
Are not already engaging in consistent moderate-intensity exercise (cutoff = 60 min/week for the past 6 months);
 
		

- 7. Present with no contra-indication to engage in regular moderate intensity exercise based on the American College of Sports Medicine guidelines. (If an individual answers yes to one item on the of the Physical Activity Readiness Questionnaire (PAR-Q), she/he will be asked to get clearance from a physician prior to participating in the study)

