A critical component of goal setting and attainment is being able to monitor progress, which can be achieved via physical activity tracking devices. Pedometer use leads to an increase in PA – they are considered acceptable and are highly useful for setting PA goals (83-85), which helps to facilitate changes in exercise behavior (86). In fact, pedometers are the most cost-effective means of increasing PA in the general population (87). In a systematic review of 26 studies, pedometer use resulted in significant increases in PA (26.9% over baseline) (70). With recent advances in sensor and Bluetooth technologies, new physical activity monitors have emerged and are currently commercially available (e.g., Fitbit), which also allow the measuring of walking intensity (e.g., through heart rate; See Section C.3.).

The model above illustrates how our proposed intervention, (PACE-Life) will lead to increased exercise and improved outcomes. Specifically, PACE-Life includes five primary components: home-based walking, group-based walking, activity tracking, goal-setting, and if-then plans, four of which impact the SDT basic needs and one of which enhances autonomous motivation. Specifically, homebased walking targets autonomy needs (as individuals can do this independently), group-based walking targets relatedness needs, and activity tracking and goal setting target competence needs. Satisfaction of each of the SDT needs leads to the intermediate target of increased autonomous motivation. PACE-Life subjects also form if-then plans which serve to enhance the impact of autonomous motivation (66, 67) and promote actual exercise behavior (56, 57). Engaging these intermediate targets in turn engenders the proximal outcomes of greater exercise participation (as measured by minutes spent walking per week and steps/day). Finally, increased exercise should lead to the improved primary outcome of CRF as well as improved secondary outcomes of loneliness, symptoms, resting heart rate, and systolic/diastolic blood pressure.

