### 3.1 OUTCOMES

The central hypothesis is that an intervention that increases physical activity as measured by minutes spent walking (at the prescribed intensity) and steps/day will result in improved health and lowered risk for premature mortality as evidenced by superior CRF (primary outcome), and on a variety of secondary outcomes (e.g. blood pressure). Guided by strong preliminary data and grounded in SDT, this hypothesis will be tested via three specific aims:

- 1. To develop a manual-based walking intervention for individuals with SSDs: PACE-Life. The manual will include guidelines for goal setting and translating intentions into behaviors (i.e., "if-then" plans), instructions for the group-based walking activity and home-based walking activity (which includes Fitbits), and increasing exercise intensity in a step-wise manner.
- 2. To examine the feasibility of implementing PACE-life at a community mental health clinic, and in a home-based virtual capacity, in a randomized controlled trial of 56 individuals with SSDs.
- 3. We will also examine the impact of PACE-life on intermediate targets (autonomous motivation and SDT needs), proximal outcomes (minutes spent walking and steps/day), the primary outcome of CRF, and secondary outcomes.

We hypothesize that PACE-life will be associated with:

- Improved proximal and primary outcomes including greater minutes/week spent walking and steps/day and increased CRF at mid-treatment (3 months), post-test (6 months), and one-month follow-up;
- Decreases in secondary outcomes including loneliness, SSD symptoms, resting heart rate, and blood pressure at mid-point, post-test, and one-month follow-up.
- Higher levels of theoretically-relevant, intermediate targets (autonomous motivation and SDT needs) at mid-treatment, post-test, and one-month follow-up.

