### 5 STATISTICAL ANALYSES

### **5.1 DATA ANALYTIC PLAN**

Feasibility will be defined by our ability to meet our recruitment targets (56 people), frequency of engagement in the intervention by participants (group attendance and activity tracking/home-based adherence), and feedback on the intervention from participants. Feedback from participants will be incorporated into modifying the manual for the RCT and/or future interventions.

Analyses of intermediate and primary outcomes will primarily be descriptive in nature. We will calculate means, standard deviations, and within-group effect sizes of intermediate targets (SDT needs and autonomous motivation), proximal outcomes, including minutes spent walking, and steps/day, the primary outcome of CRF, and the secondary outcomes including RHR, blood pressure, loneliness, and symptoms. Further, we will calculate the percentage of the sample meeting the threshold for clinically significant changes in our outcomes of 6MWT, steps/day, and minutes spent walking to determine whether these changes are clinically meaningful. Finally, we will explore the relationship between baseline IQ, treatment adherence and outcome improvement so as to determine if cognitive functioning is associated with treatment response.

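### Fitbit minutes and steps/day mix supervised group walks with independent walking, so a gain during treatment or a fall afterwards cannot by itself be read as a change in independent walking

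*Combined protocol and SAP*

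**What the plan says.** - **Source of the outcomes.** Section 4.2.2: "We will utilize data recorded from Fitbits to assess minutes spent" walking. For steps: "We will also collect daily step numbers using Fitbit data downloaded onto study laptops from Fitbit.com at group sessions". The Synopsis has the same device "track daily steps, minutes spent walking, and monitor HR throughout exercise sessions". Nothing says whether supervised sessions count, which days make up a time point, or how much wear is needed.
- **Who has group walks.** Section 4: subjects "will be assigned to the fitbit only group (control) or the PACE-Life walking group". The schedules in Section 4.1 give two group sessions a week up to their last row. Controls have none, and none is described for the follow-up month.
- **What the outcomes stand for.** Section 1 puts them downstream of autonomous motivation and if-then plans: "Engaging these intermediate targets in turn engenders the proximal outcomes of greater exercise participation (as measured by minutes spent walking per week and steps/day". The same section names failure to sustain exercise after a programme ends as a problem to solve.
- **How they are used.** Section 3.1 hypothesises "greater minutes/week spent walking and steps/day and increased CRF at mid-treatment (3 months), post-test (6 months), and one-month follow-up". Section 5.1 plans descriptive summaries with within-group effect sizes, and will "calculate the percentage of the sample meeting the threshold for clinically significant changes in our outcomes of 6MWT, steps/day, and minutes spent walking". Section 5.2 refers to comparing the groups at end of treatment or follow-up.
- **Timing.** The Synopsis (4 months plus 1) and Section 4 (16 weeks) disagree with the 24-week in-person table in Section 4.1 and the 6-month post-test in Section 3.1.

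**The concern.** One variable carries two kinds of walking: sessions that staff schedule and lead, and walking that subjects do on their own. The mix differs between arms, because controls have no groups. It also changes over time within the PACE-Life arm: no groups at baseline, two a week during treatment, none described at follow-up.

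Two statements the trial will want to make are therefore ambiguous. A higher PACE-Life mean during treatment could reflect attendance, more independent walking, or both, yet the model in Section 1 would take it as evidence that motivation was turned into action. A drop from treatment to follow-up could be the end of the groups, a loss of independent walking, or both, and could be taken for failed maintenance. The responder percentages during treatment carry the same mixture.

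**Working it through.** **Inputs.** The session numbers and lengths come from the two tables in Section 4.1, the 84% pilot attendance from the text of Section 4.1, and the 150 min/week goal from Section 2.1. Cadence, standard deviations and substitution are not in the documents; they are assumptions, shown as ranges.

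**1. The plan's own target.** Weekly minutes = (group + home sessions) x length. In virtual weeks 13-16 and in-person weeks 19-24: (2 + 3) x 30 = 150, which reproduces the goal. Groups supply 60 of the 150. The in-person table reaches only (2 + 2) x 30 = 120 at week 16.

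**2. Group share of prescribed minutes.** Weeks 8 and 12 are the halfway points of 16 and 24 weeks.

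| Schedule, week | Group | Home | Total | Group share |
|---|---|---|---|---|
| Virtual, 8 | 50 | 50 | 100 | 50% |
| Virtual, 16 | 60 | 90 | 150 | 40% |
| In person, 8 or 12 | 60 | 30 | 90 | 67% |
| In person, 16 | 60 | 60 | 120 | 50% |
| In person, 24 | 60 | 90 | 150 | 40% |

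Over the whole schedule, groups are 1440 of 2520 min in person (57%) and 790 of 1560 min virtually (51%). In the opening weeks of both they are 100%. The Home column is the prescribed walking that an out-of-session measure would retain.

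**3. Minutes from attendance.** 0.84 x 50 = 42.0 min/week (virtual week 8); 0.84 x 60 = 50.4 min/week at the other weeks in the table.

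**4. Substitution.** If a fraction s of this replaces other walking, the net is 50.4 x (1 - s): 37.8 at s = 0.25, 25.2 at 0.50, 0 at 1.

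**5. Standardised size, minutes.** With an assumed SD of 60 to 150 min/week and no substitution: 50.4/60 = 0.84 down to 50.4/150 = 0.34.

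**6. Steps, in-person walks.** Assuming 80 to 120 steps/min: 50.4 x 80 / 7 = 576 to 50.4 x 120 / 7 = 864 steps/day. With an assumed SD of 2000 to 4000 steps/day, this is 576/4000 = 0.14 to 864/2000 = 0.43. Section 5.2 gives pilot effects on steps of 0.50 to 1.03.

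**7. What a fall could mean.** Take a subject at virtual week 16 with 84% attendance, all home walks done, no other walking, and sessions recorded in full: 50.4 + 90 = 140.4 min/week. If the 90 min continue unchanged after the groups stop, the recorded total falls by 50.4/140.4 = 36% although independent walking has not changed.

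**8. Timing.** A 6-month post-test is at about week 26 (6 x 52/12), after the last row of both schedules (weeks 16 and 24). A post-test at 16 weeks or 4 months falls at the end of the 16-week schedule, or at week 16 of the 24-week one. Whether groups are in the post-test window therefore depends on which statement governs and on a window that is not defined. If they are not, the change in composition falls between mid-point and post-test instead.

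**The case against.** The strongest reply is that total walking is what the plan means to measure. Section 1 defines the proximal outcome as exercise participation and makes it the step that leads to fitness. Group walking is one of the five components of the intervention, attending it is voluntary exercise, and the 150 min/week goal is reached only by counting it. This stands: the totals are valid, and delivered walking is part of the treatment effect. It does not make the totals a measure of independent walking.

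Second, group attendance and home adherence are tracked separately (Sections 3 and 5.1). They are, and they help, but as feasibility and tolerability items. They are not carried into the proximal outcomes and have no counterpart in controls.

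Third, the analysis is mainly descriptive and within-group. That does not remove the issue, since a baseline-to-treatment change within the PACE-Life arm contains the same attendance component.

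Two stronger readings are tempting, and the documents support neither:

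- A reader might infer that the arm difference and its later fall arise by construction. Only one component does. Home walks of 30 to 90 min/week are also prescribed from mid-treatment on, real behaviour change may add to them, and substitution could shrink the group component to zero. On the assumed ranges, the step effect from attendance stays below the pilot effects.
- A reader might infer that the trial cannot tell whether PACE-Life changed independent walking. It can at follow-up: no groups are described then, so the change from baseline and the arm contrast are free of them.

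Finally, virtual sessions are stationary exercises (Section 2.1), and the documents do not say whether a wrist device records them as walking.

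**Conclusion.** The point holds as a limit on interpretation. During treatment, Fitbit minutes and steps/day include supervised sessions that only one arm receives. From mid-treatment on these are 40% to 67% of prescribed minutes, or about 42 to 50 min/week at 84% attendance. Those minutes assume that trial attendance matches the pilot, that sessions are recorded in full, and that no other walking is displaced. The standardised sizes rest on assumed SDs, and the step figures on an assumed cadence as well; they show only that the component could be material.

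A gain during treatment, or a fall from treatment to follow-up, therefore does not by itself show a change in independent walking or support the motivation model. The follow-up comparisons are free of group sessions, provided that the baseline window, once defined, closes before the first group. The 6MWT is not affected.

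**What to change.** In Section 5.1:

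1. Keep total minutes and steps/day as the proximal outcomes and for the clinically-significant-change percentages.
2. Report beside them, by arm and time point, out-of-session minutes/week and steps/day. Remove the windows of attended sessions where time-stamped Fitbit data exist; otherwise use non-group days, with matching weekdays for controls.
3. Use the out-of-session version for statements about independent walking during treatment and for post-test versus follow-up.
4. Define the Fitbit window for each time point (which days, and the minimum wear), and state whether virtual sessions count as walking.
5. Reconcile the 16-week/4-month timing (Synopsis, Section 4) with the 24-week/6-month timing (Sections 3.1 and 4.1), so that it is clear whether groups run in the post-test window.

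The cost is one added derived measure for each outcome, from Fitbit and attendance data already being collected. The non-group-day version rests on fewer days, is noisier, and may over-represent home walks if subjects place them on days without a group. Time-stamped data avoid most of this, but Section 4.2.2 mentions only daily numbers for steps, so their availability should be checked first.
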